6.3.2 Open-label Treatment Period

After the 2 days of the Month 12 DBPCFC, at Visit 13, all subjects (Part A and Part B) were to continue treatment with Viaskin Milk in an open-label manner, at the highest

dose of Viaskin Milk selected for Part B (500 µg of cow's milk protein), based on safety data of Part A subjects. The Viaskin Milk open-label treatment period was to continue until Month 24 for all subjects and until Month 48 for the subjects who entered the study extension. If a subject experienced reactions after the DBPCFC at Visit 13 that warranted postponing the application of the first patch of the open-label treatment period, it was permitted, at the discretion of the Investigator, to delay the application of the first patch of the open-label treatment up to a maximum of 7 days after Visit 13.

To increase the safety of subjects at the beginning of the open-label treatment period, in particular for subjects crossing over from placebo to the active Viaskin Milk treatment, the daily duration of application was again to be adapted from Visit 13 for the first weeks of treatment as follows:

- 6 hours of daily application during the first week
- 12 hours of daily application during the second week
- 24 hours of daily application from the third week onwards

At the time of Protocol Amendment 5, all subjects were currently receiving active treatment with Viaskin Milk 500 µg. **The switch to Viaskin Milk 300 µg will not require a progressive increase of application duration, and all subjects will be able to start with 24 hours of daily application of Viaskin Milk 300 µg.**

During the open-label treatment periods with Viaskin Milk 500 µg and Viaskin Milk 300 µg, the daily duration of patch application could also be reduced/adapted and progressively extended up over a few days to reach the 24-hours/day application in some specific cases, as described in the previous section, if the Investigator considers this could allow for an optimal management of the safety of the subjects. In the rare event that Grade 4 local skin reactions or other local AESI occur, subjects should transiently discontinue patch application. Subjects should then visit the site for the next patch application and for adequate examination and treatment of the wounded zone. Subjects should remain at the site for 1 hour before being discharged. The site staff should contact the subject via telephone the next day after removal of the patch to ensure that there are no additional local vesicles, blisters or other lesions evocative of skin disruption noted and the treatment with the patch can proceed as planned. The zone with vesicles or lesions should not be used for patch application until the zone has completely healed.

The application of the patch with regard to the location (back or arm) and zones together with the recommendations for applying and removing the patch should continue as described above in the blinded treatment period section (refer to [Section 6.3.1](#)).

If the patch was removed or has fallen off prematurely, the daily duration of application of the patch and the reason for early removal will be recorded in the subject diary cards. During the open-label treatment periods with Viaskin Milk 500 µg and Viaskin Milk 300 µg, the subjects will only record the days and time periods when the duration of application did not follow the durations recommended in the protocol. During the period of 24 hours of daily application, flexibility between 20 to 28 hours of daily application is permitted.

For subjects who terminated the study at Month 24, the last patch application was to be the day before the second Month 24 DBPCFC (day before Visit 17). For subjects who entered the study extension after Month 24, the open-label treatment period was to continue with Viaskin Milk 500 µg until Month 48. For those subjects, the last patch application was to be on the day before the second Month 48 DBPCFC (day before

Visit 23). The last application of Viaskin Milk 300 µg will depend upon the participation of the subject in the DBPCFC performed after 24 months of treatment:

- If the subjects perform the DBPCFC, the last patch application will be the day before the second day of the DBPCFC/Visit S7;
- If the subjects do not perform the DBPCFC, the last patch application will be the day before Month 24/Visit S6.

6.4 ***Blinding***

Double-blind, placebo-controlled treatment period up to Month 12

This is a randomized, double-blind study. The subject, Investigator, medical monitor, sponsor, and the entire study processing team will remain blinded to treatment assigned (refer to [Section 6.1](#), Method of Assigning Subjects to Treatment Groups) to the subjects during the 12-month double-blind treatment period and the blinding will remain until all 12-month data are collected.

The appearance of Viaskin Milk and placebo patches will be identical. During the blinded treatment period, an Emergency Code Break procedure will be available to Investigators via IWRS, to allow for unblinding a subject or treatment kit, (ie, informing the Investigator of the treatment group to which the subject has been assigned). The blind for a specific subject can be broken by the Investigator only if the Investigator considers the information indispensable to the safety of the subject. If possible, the medical monitor at the CRO and the sponsor should be consulted before breaking the blind and the Investigator should always assess the relationship of the AE to the investigational product before breaking the blind.

Open-label treatment period with Viaskin Milk 500 µg and Viaskin Milk 300 µg

After the Month 12 DBPCFC and study procedures have been completed (Visit 13), all subjects were to continue treatment until Month 24 with Viaskin Milk in an open-label manner, at the highest dose of Viaskin Milk selected for Part B (500 µg of cow's milk protein), based on safety data of Part A subjects. Treatment with open-label Viaskin Milk 500 µg was to continue until Month 48 for subjects who enter the study extension.

After the switch to Viaskin Milk 300 µg, subjects will receive this treatment in an open-label manner for 24 months.

6.5 ***Prior and Concomitant Therapy***

6.5.1 Prior and Concomitant Therapy Records and Recommendations

All prior medications used within 6 months prior to Visit 1 will be recorded on the electronic case report form (eCRF). All medications taken any time from the study start until the end of the study will be recorded on the eCRF.

Application of a topical corticosteroid to treat any local AE (eczematous lesions, pruritus, edema, etc) is allowed and will be recorded as concomitant medication. A topical medication with 1% hydrocortisone or equivalent will be distributed to each randomized subject at discharge on Day 1 (Visit 4). In case the 1% hydrocortisone topical medication is not sufficient to treat the local reaction, a topical medication containing a more potent corticosteroid can be prescribed and locally applied.

Oral antihistamine or oral corticosteroids are allowed to treat AE(s) determined as being allergic reactions and should be recorded as concomitant medications. These treatments should be limited in duration and stopped as soon as the AE(s) has (have) resolved. The Investigator will determine the best choice of treatment(s), the dose and the regimen according to the subject's age, and the type and the degree of severity of the reaction. Cetirizine is recommended as the oral antihistamine of choice.

Intramuscularly injectable epinephrine CCI

██████████ will be distributed to each subject at discharge on Day 1 (Visit 4) to be used in case of symptoms of anaphylaxis. The Investigator will explain to the subject and/or parent(s)/guardian(s) and document when and how to (self) inject the epinephrine according to the Anaphylaxis Emergency Action Plan (see [Appendix 14.5](#)), which will also be given to the subject. The intramuscularly injectable epinephrine will be replaced if used or if it expires. Any use (ie, administration) of injectable epinephrine within 6 months prior to Visit 1 or during the study must be recorded into the eCRF.

The administration of prior/concomitant medications must be recorded in the eCRF to include the medication name, dosage and units, route, schedule, start and stop dates (when applicable), and indication for use. Generic names for concomitant medications should be used or alternatively Trade names should be used in the case of combined medications.

6.5.2 Prohibited Concomitant Treatments and Procedures:

- Any investigational drug or device other than Viaskin Milk or placebo.
- Short-acting antihistamines for 1 to 3 days and long-acting antihistamines for 5 to 7 days before any DBPCFC or SPT procedures (see [Appendix 14.7](#)).
- Long-acting β_2 agonists (eg, formoterol) within 36 hours before any DBPCFC.
- Omalizumab or other immunomodulatory agents.
- Biological drugs including but not limited to antibodies, B-cells depleting agents or tumor necrosis factor inhibitors.
- Calcium channel blockers.
- Beta-blockers or ACE inhibitors.
- Any other immunotherapy treatment (eg, food allergen[s] or aeroallergen[s]).
- Before Protocol Amendment 5: Any food challenge to milk (other than required as per this protocol) or to any other food.
- After Protocol Amendment 5: Any food challenge to milk (other than proposed as per this protocol)

6.5.3 Permitted Concomitant Treatments and Procedures:

- Topical corticosteroids to treat any local cutaneous AE (eg, eczema or erythema, pruritus, edema, rash, etc).
- Oral antihistamines and oral or inhaled corticosteroids to treat AEs (see [Section 7.3.2.3.3, Rescue Medication](#)). Duration of treatment should be limited and ideally stopped upon AE resolution. An inhalation corticosteroid conversion table is included in [Appendix 14.6](#).
- Intramuscularly injectable epinephrine.

- Treatments (other than those described above) prescribed in case of any AE.
- After Protocol Amendment 5: Any food challenge to any other food than milk required for the subject's medical management will be permitted. Whether the subject's medical condition is still compatible with their participation in the study should be assessed by the Investigator and the Sponsor's medical monitor before the food challenge is performed. Note that the initiation of any other immunotherapy treatment remains prohibited during the participation of the subject in the MILES study (refer to [Section 6.5.2](#)).

6.6 Treatment Compliance

Subjects and/or parent(s)/guardian(s) will receive diary cards to record the daily application of Viaskin patches (see [Section 7.3.2.12](#) for further details about diary cards). The duration of the patch application will be recorded every day from Day 1 (Visit 4) up to Month 3 (Visit 9) on the subject diary cards. After Month 3, the subjects will only record the days and time periods when the duration of the patch application did not follow the durations recommended in the protocol. During the period of 24 hours of daily application, flexibility between 20 to 28 hours of daily application is permitted. If a Viaskin patch is removed prematurely or falls off, the daily duration of application of the patch and the reason for early removal will be recorded in the subject diary cards. The data recorded in the diary card by the subject and/or parent(s)/guardian(s) will be collected periodically during the subject's visit at sites and entered into the eCRF or the clinical database.

It is the Investigator's responsibility to correctly instruct subjects and/or parent(s)/guardian(s) on how to store and administer the investigational product. At each visit, prior to dispensing a new investigational treatment box, the compliance of the subject will be assessed by evaluating the number of days the patches were applied (even for a duration that is less than the recommended duration), *versus* the number of days in that time interval. An overall compliance of $\geq 80\%$ over the treatment period is sought. Subjects exhibiting a poor compliance ($< 80\%$) should be counseled on the importance of a good compliance.

The Investigator or designated study personnel will maintain a log of all investigational product dispensed (see [Section 10.1](#), Drug Accountability for details).

6.7 Study Stopping Rules

Study enrollment will be suspended pending an expedited safety review by an independent DSMB, if any of the following occur:

- Any death related to Viaskin dosing;
- More than one Stage 3 anaphylaxis (see [Appendix 14.4](#), Anaphylaxis Staging System) related to Viaskin application (and not occurring during the DBPCFCs);
- More than 3 subjects requiring > 1 injection of epinephrine related to Viaskin application (and not occurring during the DBPCFCs).

Upon safety review, 1 of the following outcomes will be determined:

- Accrual into the study may continue without modification;
- Accrual into the study may continue with modifications as recommended by the DSMB;
- Accrual into the study should stop.

7 Study Procedures

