4.5 Removal of Subjects from Therapy or Assessments

Subjects who are withdrawn from the study will not be replaced. Participation of a subject in this clinical study may be discontinued for any of the following reasons:

- Adverse Event: any SAE, clinically significant AE, or severe laboratory abnormality.
- Subject or parent(s)/guardian(s) decision (consent withdrawal).
- Investigator decision: occurrences of any medical condition or circumstances that expose the subject to substantial risk and/or do not allow the subject to adhere to the requirements of the protocol.
- Pregnancy.
- Noncompliance: subject's failure to comply with protocol requirements or study-related procedures.
- Lost to follow-up: subject's failure to return for scheduled visits despite telephone or written attempts of contact.
- Sponsor or regulatory authority decision: termination of the study by the sponsor, FDA, or other regulatory authorities.
- Death.

Subjects and their parent(s)/guardian(s) are free to withdraw consent from participating in the study at any time without prejudice to further treatment. The reason(s) for withdrawal will be documented. Subjects withdrawing from the study should complete the early termination study procedures ([Section 7.2.5](#)).

Reasonable efforts will be made to contact subjects who are lost to follow-up and will be documented in the subject's file.

Subjects who are withdrawn from the study will receive standard of care according to the judgment of the treating physician.

The sponsor has the right to terminate the study under special circumstances that may be related to the investigational product or the company or for any other reason. In these instances, the Investigators and the regulatory authorities and Institutional Review Boards (IRBs) will be informed about the reason of study termination.

Stopping rules for the study are presented in [Section 6.7](#).

5 *Investigational Products*

5.1 *Drug Substance*

The drug substance is an unmodified allergen extract that is a lyophilized cow's milk proteins extract. **CCI** [REDACTED]

[REDACTED]

5.2 *Investigational Products Administered*

The investigational product Viaskin Milk (DBV135) patch consists of an epicutaneous drug delivery system (EDS), with the appearance of a patch, containing a solid deposit of cow's milk proteins. **CCI** [REDACTED]

[REDACTED]

[REDACTED]

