2.2 TIMINGS OF ANALYSES

2.2.1 Primary analysis and subsequent analyses

The primary analysis of safety and efficacy was performed at the end of the double-blind period, after all randomized subjects had completed the Month 12 Double-Blind Placebo-Controlled Food Challenge (DBPCFC), or withdrew.

After month 12, all subjects continued treatment with Viaskin Milk 500 μ g dose in an open-label manner for up to a maximum of 36 additional months. After the analysis of the double-blind period that showed the best efficacy with the Viaskin Milk 300 μ g dose, subjects were switched to the 300 μ g dose and continued treatment for two additional years.

Following the month 12 double-blind period primary analysis, three subsequent analyses will be conducted during the open-label treatment periods:

1. OL-500 period analysis: when all randomized subjects completed the Viaskin Milk 500 μ g open-label period, or withdrew.
2. OL-300 period Year 1 analysis: when all randomized subjects completed one year of Viaskin Milk 300 μ g open-label period, or withdrew (see [Table 1](#)).
3. OL-300 period (Year 2) final analysis : when all subjects completed the End of Study (EOS) visit, or withdrew. The complete analysis as described in this SAP will be performed.

This current SAP v7.0 describes in particular the analyses that will be done for the first year and at the end of the OL-300 period.

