Subjects from both Part A and Part B were randomized to receive treatment with Viaskin Milk or placebo for 12 months (randomized double-blind treatment period), after which a second DBPCFC was performed. The primary analysis of this study was conducted after data have been collected up to Month 12 visits including both days of the DBPCFC at Month 12. Consequently, results from the safety and efficacy data collected in all Part A and Part B subjects up to and including the Month 12 visits were reported in the 12-Month Clinical Study Report (CSR).

This document is confidential

Statistical Analysis Plan

After the Month 12 DBPCFC, all subjects from Part A and Part B were to continue treatment with active Viaskin Milk 500 μ g, the highest dose determined to be safe, for up to a maximum of 36 months (DBPCFCs at Month 24, 36 and 48). Following results of the 12-month blinded period, all eligible subjects who wish to continue participation in the study switched from Viaskin Milk 500 μ g to Viaskin Milk 300 μ g for 24 additional months of treatment, as per protocol Amendment 5, independently of the duration of previous treatment (Optional DBPCFC at 12 and/or 24 months after switch to Viaskin Milk 300 μ g dose).

A final End-of-Study (EOS) visit will be performed for all subjects when they completed or stopped the study. The EOS visit was to take place 2 weeks after the last DBPCFC at Month 24 for the subjects completing the study at Month 24, or 2 weeks after the last DBPCFC at Month 48, for subjects completing the study extension at Month 48. For subjects switching to Viaskin Milk 300 μ g, the EOS visit will take place 2 weeks after the end of the 24-month treatment period at this dose.

Three-hundred-and-eight children and adolescent subjects have been screened, 198 were randomized in this study, 18 subjects in Part A and 180 subjects in Part B. In Part B, the randomization was stratified by site and by age group (children 2 to 11 years old at the time of Visit 1; adolescents 12 to 17 years old at the time of Visit 1).

The total duration of the study will be approximately 6 years and the total duration of participation in the study will differ for each individual subject and could be up to approximately 6 years.

[Figure 1](#) of the study protocol version 6.0 presents a summary of the enrolment process into Part A and Part B of the study, and [Figures 2](#) and [3](#) present the overview of the study design.

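### Once the last subject was randomised, a section 6.7 trigger still starts an expedited DSMB review, but the rule names no outcome for subjects still applying patches

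*Protocol*

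**What the plan says.** Protocol section 6.7 lists three study-level triggers: a death related to Viaskin; a second related Stage 3 anaphylaxis; and a fourth subject needing more than one epinephrine injection for a related reaction. The second and third exclude events during food challenges. None is limited to a study period.

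The consequence of a trigger is "Study enrollment will be suspended pending an expedited safety review by an independent DSMB, if any of the following occur". The review then has three possible results. Accrual may go on unchanged; or "Accrual into the study may continue with modifications as recommended by the DSMB"; or "Accrual into the study should stop".

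Section 4.5, on removing subjects from therapy or assessments, treats this as the rule for the whole study: "Stopping rules for the study are presented in" section 6.7. The same section lists, among reasons for ending participation, "Sponsor or regulatory authority decision: termination of the study by the sponsor, FDA, or other regulatory authorities".

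On timing, SAP section 3.1 reports that "198 were randomized in this study, 18 subjects in Part A and 180 subjects in Part B". SAP section 2.2.1 places the primary analysis "after all randomized subjects had completed the Month 12 Double-Blind Placebo-Controlled Food Challenge (DBPCFC), or withdrew". Protocol section 6.3.2 adds: "At the time of Protocol Amendment 5, all subjects were currently receiving active treatment with Viaskin Milk", at 500 µg.

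**The concern.** A stopping rule should say what happens to the people exposed to the risk. Here both the action and the outcomes are directed at people not yet in the study. Once enrolment has ended, even the strictest outcome stops something that has already stopped.

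The subjects left are children on active treatment at home. In the 300 µg period, kits are dispensed at Visits S1, S2, S3 and S5, about six months apart, so a family may hold several months of patches. Patch use therefore continues unless someone instructs otherwise. If a trigger is met, section 6.7 does not say whether the other children keep applying patches while the review runs, who decides that, or what the review may conclude for them. Investigators and IRBs work from the protocol, and section 4.5 sends them to this section.

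**Working it through.** No sample-size or error-rate figure bears on this point. The check is a side-by-side reading with a little arithmetic.

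**1. Do the triggers still apply after enrolment?** Yes. Section 6.7 has no period limit, and its only exclusion is for reactions during food challenges. A trigger in any later period still calls for the expedited DSMB review.

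**2. What does a trigger do automatically?** One thing: it suspends enrolment. No hold on dispensing or patch application is named.

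**3. What may the review conclude?** All three outcomes have accrual as their subject. The second allows modifications of any kind, so it could reach treatment in practice, but it is framed as a condition on continuing accrual. The third stops accrual only.

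**4. When did enrolment end?**
- Planned (protocol section 8.4): 18 + 176 = 194.
- Randomised (SAP section 3.1): 18 + 180 = 198, which is 4 more, or 4/194 = 2.1% above plan.
- The primary analysis followed Month 12 completion or withdrawal of all of them, and the 300 µg switch followed that analysis.

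Enrolment therefore closed before the 300 µg period. It must also have closed while the last-randomised subjects were still in blinded treatment.

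**5. Could enrolment be read to include the switch to 300 µg?** Not naturally. Protocol section 4.2 uses the term for initial entry, while the switch has its own criteria in section 4.4.

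**6. How long is the rule without an object?** From the last randomisation. For the last-randomised subject who switches and completes: 12 months double-blind + 24 months at 300 µg = 36 months, plus any time on open-label 500 µg.

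**7. What else applies when a trigger is met?**

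| Trigger | Other provisions |
|---|---|
| Related death | An SAE (section 7.3.2.2.1), reported within 24 hours (7.3.2.2.2) |
| Second related Stage 3 anaphylaxis | Severe anaphylaxis on the same Appendix 14.4 scale is an important medical event, so also a 24-hour SAE |
| Fourth subject needing more than one epinephrine injection | Partial overlap: an anaphylactic reaction needing three or more epinephrine uses is an SAE; a systemic hypersensitivity reaction treated with epinephrine is an AESI (7.3.2.5) |

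The DSMB reviews safety at intervals and ad hoc (protocol section 3.1.1) and makes recommendations on study conduct (SAP section 2.2.2). An affected subject can be withdrawn (section 4.5) or have patch use shortened or interrupted (6.3.1, 6.3.2). What these provisions do not supply is a stated decision, following a trigger, on patch use by the other treated subjects.

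**The case against.** The strongest reply is that the omission is one of wording. Section 6.7 itself calls in the DSMB, and that board's remit is not confined to accrual: SAP section 2 credits it with permitting the switch to 300 µg for subjects already on treatment. A board convened after a related death would not feel bound to advise only on recruitment. The events behind the first two triggers are already 24-hour SAEs, the sponsor or a regulator can terminate the study, and protocol section 6.2 reports no safety concern at any dose after the blinded period. Protocol section 3.1.1 assigns the DSMB's operations to its Charter, which is where handling of treated subjects might be expected.

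Most of this stands. It rules out three stronger readings that a reader might infer:

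- *That a trigger after enrolment has no effect, or that no safeguard connects to it.* Section 6.7 starts an expedited review by a board that can recommend changes in conduct, and SAE reporting covers the first two triggers and part of the third.
- *That the gap belongs to the 300 µg period.* It opens at the last randomisation.
- *That a trigger is likely.* The documents give no basis for a probability.

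What the reply does not meet is the text of the designated rule. Termination is discretionary, withdrawal is subject by subject, and none of the provisions asks for a decision on ongoing patch use while the review runs.

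**Conclusion.** The point holds as a cheap improvement to the protocol, with moderate confidence. After the last randomisation, the one automatic action in section 6.7 has nothing to act on, and three of three outcomes concern accrual. The rule therefore prompts a review without naming an outcome for subjects still on patches, for at least 36 months in the last-randomised subject who completes.

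This rests on reading enrolment as protocol section 4.2 uses it, and on the protocol and SAP alone. If the Charter already sets out how treated subjects are handled after a trigger, what remains is to align the protocol with it. The documents do not show that children were left unprotected, and the point has no bearing on the efficacy analyses.

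**What to change.** Keep the three triggers. Amend section 6.7 to state that, in any study period:

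1. A trigger suspends enrolment, if open, and starts an expedited DSMB review.
2. Within a stated short time, the DSMB decides whether treated subjects pause patch application while the review runs.
3. The outcomes apply to accrual *and ongoing treatment*: both may continue unchanged, may continue with changes that the DSMB recommends, or should stop.

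No special clause is needed for the switch visit, except for any subject not yet switched: the SAP describes the open-label 500 µg analysis as done, and that analysis was due only once all subjects had completed that period or withdrawn. An automatic hold on the switch would in any case leave a waiting subject on the higher dose (protocol section 3.1.4).

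Cost: a protocol amendment with IRB approval (section 11.1) across the 17 sites, a matching Charter line if the Charter lacks one, and a possible brief interruption of open-label treatment. No extra data, visits or subjects are needed.
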